24 To complete testing on the 12 volunteers necessary to reach statistical power, we estimate we will need to
25 consent 44 individuals. All screening will stop once complete data has been collected on 12 volunteers.
26 Records and specimen collection are described in the Research Procedures and Data Collection sections.
27 During briefings and consenting potential participants will be informed that even though they may be
28 eligible and want to participate, if we are able to obtain enough data from preceding subjects, they may not
29 ultimately be tested.

30 **B5.2.3 Inclusion Criteria**

31 • Men and women aged 18 – 39 years
32 • Weight stable (± 5 lbs) for at least 2 months prior to the start of the study
33 • Body mass index (BMI) between 18.5-30 kg/m²
34 • Recreationally active based on assessment of physical activity history 2-4 days per week aerobic
35 and/or resistance exercise
36 • Refrain from taking any NSAIDS (i.e., aspirin, Advil®, Aleve®, Naprosyn®, or any aspirin-containing
37 product for 10 days before and at least 5 days AFTER each muscle biopsy. (*Tylenol® or
38 acetaminophen is ok to use if needed for discomfort)
39 • Refrain from the use of alcohol and nicotine for the duration of the study
40 • Females must be on contraception (e.g., oral birth control, NuvaRing®, Depo Provera®, etc.)
41 • Supervisor approved leave status for federal civilian employees working within the US Army Natick
42 Soldier Systems Center

[figure not shown]
43 **B5.2.4 Exclusion Criteria**

- 1 • Metabolic or cardiovascular abnormalities, gastrointestinal disorders (i.e., kidney disease, diabetes, cardiovascular disease, etc.)
- 2 • Disease or medication (i.e., diabetes medications, statins, corticosteroids, etc) that affects macronutrient utilization and/or the ability to participate in strenuous exercise
- 3 • Allergies or intolerance to foods (including but not limited to lactose intolerance/milk allergy), vegetarian practices, or medications (including, but not limited to, lidocaine or phenylalanine) to be utilized in the study
- 4 • Anemia (HCT < 38) and Sickle Cell Anemia/Trait
- 5 • Abnormal PT/PTT test or problems with blood clotting
- 6 • Present condition of alcoholism, use of nutritional/sports supplements, anabolic steroids, or other substance abuse issues
- 7 • Musculoskeletal injuries that compromise the ability to exercise
- 8 • Blood donation within 8 weeks of beginning the study
- 9 • Pregnancy
- 10
- 11
- 12
- 13
- 14
- 15
- 16
- 17
- 18

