17 exertional syncope) or shows signs of poor perfusion, or if there is an equipment failure.
18

19 Muscle Biopsy

20 Percutaneous muscle biopsy will be performed to obtain skeletal muscle samples for assessment of
21 muscle glycogen, microRNA expression and molecular pathways regulating carbohydrate metabolism.
22 Muscle samples will be taken from the vastus lateralis using a 5-mm Bergstrom needle with manual suction
23 while the participant is under local anesthesia (1% lidocaine) according to the approved USARIEM SOP
24 (42, 43). Multiple passes with the biopsy needle may be necessary to obtain adequate sample with each
25 biopsy. Muscle biopsies will be conducted immediately before and after the muscle glycogen depletion
26 protocol. After the second muscle biopsy volunteers will rest and consume either a carbohydrate beverage
27 or a matched placebo. Three hours following the conclusion of the glycogen depletion protocol a third
28 biopsy will be obtained to assess the acute influence of carbohydrate intake. Volunteers will be allowed to
29 leave at this point. Volunteers will return the following morning for a fourth muscle biopsy taken at a new
30 incision site. In this same incision a fifth biopsy will be taken after 80-min of steady state exercise to
31 determine the influence of adequate or low glycogen storage on exogenous carbohydrate uptake and
32 oxidation during exercise. Following a minimum 7-d washout period, volunteers will return to the laboratory
33 to complete the second arm of the investigation. A total of ten muscle biopsies will be conducted per
34 volunteer.
35

36 Assessment of Resting Respiratory Quotient

37 Respiratory Quotient (RQ) will be measured under resting conditions before the 24-hr post glycogen
38 depletion muscle biopsy, using open circuit indirect calorimetry (Parvo Medics). Assessment of RQ will
39 allow us to determine the influence of glycogen storage on carbohydrate and fat oxidation. Measurements
40 will occur between 0500-0800-hrs following a minimum 10-hr overnight fast. Volunteers will rest in the
41 supine position for approximately 30-min prior to each measurement in a quiet and dim, temperature
42 regulated room. To minimize error, volunteers will be instructed to minimize movement once the
43 mouthpiece is inserted, or the mask/hood is placed over their heads to collect expired air. The test will be
44 discontinued when 10-min of steady state oxygen consumption (VO_2) and carbon dioxide production

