32 Hard copy data records will be stored for a minimum of three years from the time the study is completed.
33 Electronic data records will be maintained for a period of at least five years after the study has been
34 completed.
35

36 **B5.6 Managing Data and/or Human Biological Specimens for Future Research**

37 Any use of the samples outside of this defined protocol will be submitted as a protocol amendment or a
38 new protocol. Samples will be retained for future analyses once the protocol is closed if the subject
39 provided permission in the informed consent document.
40

41 **B5.8 Statistical Analysis**

42 **B5.8.1 Sample Size Estimation**

43 Statistical power and sample size were determined using the minimum fold change required for a
44 physiologically relevant difference in microRNA expression. Variance (standard deviation) was based
45 on recent publications assessing change in microRNA expression in skeletal muscle (18, 50, 51) and
46 circulating (34, 35, 52) in response to an acute bout of exercise. Using this information the sample
47 size necessary to determine statistical significance between intervention arms, with a mean fold
48

1 change of 1.5 ± 1 is 9 per group, with an alpha of 0.05 and 80% power. In the present study, 12
2 volunteers will be studied in a repeated measures crossover design to account for potential greater
3 inter-individual variability.
4

5 **B5.8.2 Data analysis**

7 Statistical analyses will be conducted using either SPSS (IBM Corp. Armonk, NY), SAS 9.3 (SAS
8 Institute Inc., Carey, NC), or equivalent. Common descriptive statistics will be used to describe
9 volunteer characteristics. Shapiro-Wilk tests will be used to determine normality of data. Mixed
10 model repeated measures ANOVA will be performed to determine main effects of time (baseline,
11 immediately, 3-hr, and 24-hr post glycogen depletion), carbohydrate intake ($6.0 \text{ g} \cdot \text{kg}^{-1} \cdot \text{d}^{-1}$ versus $1.5 \text{ g} \cdot \text{kg}^{-1} \cdot \text{d}^{-1}$) and time-by-carbohydrate interactions for skeletal muscle and circulating microRNA, mRNA
12 expression, and markers of nutritional status. If interactions are significant, Bonferroni correction will
13 be used to examine these relationships. Correlation coefficients and multiple regression analysis will
14 be used to evaluate relationships between study outcome measures. The alpha level will be adjusted

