15 for multiple comparisons, with the level for statistical significance set at $P < 0.05$.
16

20 **SECTION C: HUMAN RESEARCH PROTECTIONS**

21 **C1. RECRUITMENT AND CONSENT**

24 **C1.1 Identification and Selection of Subjects**

26 Potential volunteers will be recruited from the U.S. Army Natick Soldier Center pool of military volunteers
27 during a face-to-face briefing as described in the below *Recruitment Process* section. Additional volunteers
28 will be recruited from civilian population and active duty military stationed at the U.S. Army Natick Soldier
29 Center, as well as civilians from the local surrounding area using flyers and electronic posting (**Appendix**
30 **G**)

32 **C1.2 Recruitment Process**

34 Superiors of Service members (e.g., unit officers, senior NCOs, and equivalent civilians) / supervisors of
35 DoD civilians (e.g., military and civilian supervisors or anyone in the supervisory structure) shall not be
36 present at any recruitment sessions or during the consent process in which members of units under their
37 command / personnel under their supervision are afforded the opportunity to participate as human subjects
38 of research.

40 For Soldiers in the U.S. Army Natick Soldier Center pool of military volunteers, the Principal Investigator
41 will furnish a copy of the consent form to the Human Research Subjects Program Coordinator or designee.
42 The Coordinator will schedule the consent briefing for the military human research volunteer platoon and
43 will serve as ombudsman during the briefing. Civilians and permanent party military will be recruited for the
44 study using posted or electronically distributed or though informational briefs. Principal Investigator or
45 Project Coordinator will receive and respond to inquiries submitted from these recruitment materials, and
46 will schedule informed consent briefings for these potential volunteers. Potential volunteers not in the U.S.
47 Army Natick Soldier Center pool of military volunteers will be briefed one-on-one by the Principal
48 Investigator or Project Coordinator.

49 **C1.3 Eligibility**

1 All potential volunteers will complete the background questionnaire (**Appendix H**). Volunteers must be
2 medically cleared by the Office of Medical Support and Oversight (OMSO) for participation in accordance
3 with USARIEM procedures outlined for screening volunteers for research involving exercise. Potential

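### Holm's step-down correction would give somewhat more power than the plain Bonferroni in B5.8.2 for the comparisons after a significant interaction, at the same familywise error

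*Combined protocol and SAP*

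**What the plan says.** B5.8.2 (Data analysis) plans a mixed-model repeated measures ANOVA with time at four levels (baseline, then "immediately, 3-hr, and 24-hr post glycogen depletion), carbohydrate intake" at two levels) and their interaction. Next comes "If interactions are significant, Bonferroni correction will" "be used to examine these relationships". The section closes by saying that alpha is adjusted "for multiple comparisons, with the level for statistical significance set at" P < 0.05. It does not say which comparisons form the family, or how many there are.

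B5.8.1 (Sample Size Estimation) gives the only planning figures: a mean fold "change of 1.5 ± 1 is 9 per group, with an alpha of 0.05 and 80% power". The 12 "volunteers will be studied in a repeated measures crossover design to account for potential greater" variability between individuals. B5.2.2 adds: "All screening will stop once complete data has been collected on 12 volunteers". The analysed number is therefore 12.

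B5.3 (Muscle Biopsy) fixes when the arms start to differ: "After the second muscle biopsy volunteers will rest and consume either a carbohydrate beverage" or the matched placebo.

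**The concern.** Plain Bonferroni holds each of K comparisons to 0.05/K, however many of the others have already been rejected. In this design the family may mix three kinds of comparison:

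- changes over time after a ride to failure, which may be large;
- arm contrasts at baseline and immediately after depletion, where no difference is expected because the beverage comes after the second biopsy;
- arm contrasts at 3 hr and 24 hr, which carry the carbohydrate question.

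The last kind pays the full penalty for the whole family. Holm relaxes the threshold as comparisons are rejected, so large exercise responses would lighten the penalty on the carbohydrate contrasts. What is at stake is which specific arm contrasts can be declared significant with 12 volunteers.

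**Working it through.** **1. The plan's own figure.** A two-sample, two-sided t-test with difference 1.5, SD 1, alpha 0.05 and power 80% needs 8.06 per group, rounded up to 9 (power 0.797 at 8 and 0.848 at 9). The stated 9 is reproduced, so the planning effect is 1.5 SD at an unadjusted alpha. Sidedness is not stated; two-sided is assumed.

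**2. The two rules.** Order the P values p(1) ≤ … ≤ p(K).

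- Bonferroni rejects every p(i) ≤ 0.05/K.
- Holm rejects p(i) while p(i) ≤ 0.05/(K − i + 1), and stops at the first failure.

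Every Holm threshold is at least 0.05/K, so Holm rejects all that Bonferroni rejects. At i = 1 the two thresholds are equal, so at least one rejection occurs under Holm exactly when it occurs under Bonferroni.

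**3. Inputs.** From the documents: n = 12, two arms by four times, planning effect 1.5 SD. Assumed, because the plan gives none: equal correlation 0.5 among a person's eight samples; the same arm difference at 3 hr and 24 hr and none earlier; an exercise response of 1.5 SD at the immediate and 3-hr times in both arms; paired t-tests. The SD of a paired difference is SD × √(2(1 − 0.5)) = 1.0 SD, so an arm difference of 1.0 SD is a standardised paired effect of 1.0.

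**4. Families examined.** These are constructions, since B5.8.2 defines none.

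- K = 4: the arm contrast at each time. 0.05/4 = 0.0125.
- K = 16: those 4 plus 6 pairwise time contrasts in each of 2 arms. 4 + 12 = 16, and 0.05/16 = 0.0031.
- K = 28: all pairs of the 8 cells. 8 × 7/2 = 28, and 0.05/28 = 0.0018.

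**5. Power for each of the 3-hr and 24-hr arm contrasts** (20,000 or more simulated trials per setting; interaction gate applied only where stated):

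| Family | Arm difference | Exercise response | Bonferroni | Holm |
|---|---|---|---|---|
| 4 | 1.0 SD | 1.5 SD | 68% | 72% |
| 4 | 1.5 SD (plan) | 1.5 SD | 97% | 98% |
| 16 | 1.0 SD | 1.5 SD | 44% | 57% |
| 16 | 1.0 SD | 0.5 SD or none | 44% | 47% |
| 16 | 1.5 SD (plan) | 1.5 SD | 88% | 95% |
| 28 | 1.0 SD | 1.5 SD | 35% | 47% |
| 28 | 1.5 SD (plan) | 1.5 SD | 82% | 91% |
| 4, with interaction gate | 1.0 SD | 1.5 SD | 59% | 62% |
| 16, with interaction gate | 1.0 SD | 1.5 SD | 40% | 51% |

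The interaction test itself passes in about 79% of trials at 1.0 SD. With K = 16, 1.0 SD and no gate, the change is 28% to 37% at correlation 0.3 and 73% to 86% at 0.7.

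**6. How much of the loss comes back.** Take the plan's 1.5 SD at correlation 0. The paired effect is 1.5/√2 = 1.06, and unadjusted power is 91.6%. With K = 4, Bonferroni gives 74% and Holm 77%, so about 3 of the 17.5 lost points return. If the family were only the 3-hr and 24-hr contrasts, it would be 84% to 89–90%, which is most of the loss.

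**7. Error rate.** Under the global null the two methods have identical familywise error (0.050 for 4 independent contrasts, 0.044 at correlation 0.5). With two real arm contrasts in a family of 4 it was 0.025 for Bonferroni and 0.043 to 0.049 for Holm. Both stay within 0.05.

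**The case against.** Bonferroni is prespecified and valid under any dependence, and it gives simple simultaneous intervals. No conclusion becomes unsound by using it. That stands, and it is why the point is optional.

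The larger gains also rest on assumptions. They need a big exercise response, a wide family and an arm effect below the planning value. If only one arm contrast is real, the gain in a family of 4 is nil (68.3% to 68.5%). In a family of 16 with the large exercise response it is 44% to 52%. This stands too, and the size has to be given as a range.

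Family size moves Bonferroni power from 68% to 44% to 35% across K = 4, 16 and 28, which is more than the change of method does at any one K. The undefined family is therefore the larger gap in the same sentence. That is correct, and Holm cannot be applied until the family is listed.

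A reader might infer that carbohydrate-responsive microRNAs missed by Bonferroni never reach the serum assays or the pathway analysis. The documents do not support this. B5.4, under mRNA and microRNA Expression and under Bioinformatics Analysis, carries forward any microRNA whose expression changed significantly, without naming a contrast. By step 2, the two methods agree on whether a microRNA has at least one significant comparison, and they agreed in every simulated trial. The panels would differ only if selection were tied to particular arm contrasts within a wider family, which the plan does not say.

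**Conclusion.** The point holds as an optional efficiency improvement, not as an error in the plan. Holm is never worse than Bonferroni in what it rejects, and it keeps the 5% familywise error. Its benefit lies in which specific 3-hr and 24-hr arm contrasts are declared significant.

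The gain is about 1 to 4 points per contrast for four arm contrasts. For 16 comparisons it is 7 to 13 points when the exercise response is large, and about 3 points when it is small or absent. The interaction gate lowers absolute power and trims the gain somewhat. It would overstate the case to say that Holm restores the power Bonferroni loses: with four contrasts it returns a minority. These figures rest on the assumed correlations, exercise response and families.

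**What to change.** In B5.8.2, replace the Bonferroni correction with the Holm step-down Bonferroni correction for the comparisons after the interaction test. List the comparisons that make up the family, and report Holm-adjusted P values.

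The cost is a short change of wording, with no new data, volunteers or biopsies. The one downside is that simultaneous confidence intervals are less direct than under plain Bonferroni; unadjusted intervals, labelled as such, can be shown beside the adjusted P values.

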
B3. MILITARY RELEVANCE

Military personnel often engage in sustained physical activity while time to eat and availability of food is limited (4, 36, 37). Under such conditions, it is likely that skeletal muscle glycogen stores are depleted, reducing the service member's ability to maintain an optimal level of physical performance. However, during 'real-world' military training operations there is limited knowledge regarding altered carbohydrate metabolism at the skeletal muscle level, as invasive investigations requiring muscle biopsies cannot be conducted during training operations. Identifying the mechanism, as well as determination of non-invasive markers of molecular pathways regulating carbohydrate metabolism is critical to move findings from controlled laboratory settings to field operations. Modeling of circulating microRNA may allow for a more comprehensive understanding of nutrient adequacy during military operations, allowing for implementation of targeted nutrition interventions to optimize military performance. Support for this protocol comes from Defense Health Program (DHP) Research funds, under Joint Program Committee-5 Nutrition and dietary supplements working group.

B4. OBJECTIVES/SPECIFIC AIMS/RESEARCH QUESTIONS

Objectives

1. Determine the influence of carbohydrate availability (e.g., glycogen depletion and repletion) on skeletal muscle microRNA expression, and if changes in circulating microRNA are reflective of changes in skeletal muscle microRNA.

1 2. Determine how initiation of exercise with adequate or low glycogen stores effects exogenous
2 carbohydrate efficiency.

3

4 **Hypotheses**

5

6 1. Expression of microRNA in skeletal muscle will be influenced by alterations in glycogen status, and
7 that these changes in skeletal muscle microRNA will be associated with modulation in circulating
8 microRNA.

9

10 2. Exogenous carbohydrate efficiency will be greater when exercise is initiated with lower glycogen
11 stores. Increased efficiency will be associated with higher phosphorylation of IRS-1 and AMPK.

12 **B5. RESEARCH PLAN**

13

14 **B5.1 Research Design**

15 This study will be a randomized cross-over placebo control trial.

16

17 **B5.2 Research Subjects/Population(s)**

18

19 **B5.2.1 Subject Population(s)**

20 Subject population will be representative of active duty male and female service members, being in good
21 health and recreationally active.

22

23 **B5.2.2 Number of Subjects, Records, and/or Specimens**

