Following identification of skeletal muscle microRNA that had a significant change, Taqman® probes (Applied Biosystems) will be used to assess the expression of these microRNA in serum to determine their potential use as noninvasive markers of altered carbohydrate metabolism following glycogen depletion and repletion. Total circulating miRNA will be extracted from 200 μ L serum using miRNeasy Serum/Plasma kit, which allows for extraction and purification of small (< 200 nt) cell-free RNA (Qiagen, Valencia, CA, USA). Exosomal circulating miRNA will also be extract from 1000 μ L serum using miRCURY™ RNA Isolation Kit to measure miRNA. To avoid introduction of potentially contaminating material, prior to RNA extraction serum samples will be centrifuged for 10 min at 4°C to remove cellular debris. Supernatant will be removed and transferred to a new tube without disturbing the pellet. Due to the small amount of RNA in the serum, 3.5 μ L of a Spike-In Control (C. elegans miR-39; Qiagen) will be added to all samples prior to extraction of RNA to determine the yield of template recovered. After extraction 3 μ L of serum RNA will be reverse transcribed using the TaqMan® microRNA RT kit (Applied Biosystems) with miRNA-specific stem-loop RT primers pooled in 1X-Tris-EDTA (TE) buffer for a final dilution of 0.05X. A pre-amplification step will be performed after reverse transcription to increase cDNA template using a primer pool of 20 X Taqman® Small RNA Assays (Applied Biosystems) for miRNA of interest at 0.05X concentration in 1X TE buffer. All serum miRNA will be normalized to the geometric of external (Spike-In Control C. elegans miR-39) and internal controls to allow for both technical and inter-individual normalization (47). Geometric mean of controls will be used to correct for possible outlying values and abundance differences between the different controls (48).

All reverse transcription for mRNA and miRNA, and pre-amplification of serum miRNA will be conducted in a T100™ Thermal Cycler (Bio-Rad, Hercules, CA). A StepOnePlus™ real-time PCR system (Applied Biosystems) will be used to perform all mRNA and miRNA analysis. Fold changes will be calculated using the $\Delta\Delta C_T$ method as described below in statistical analysis section.

Bioinformatics Analysis

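### B5.8.2 leaves the unit of analysis for the serum–muscle microRNA association unstated: ordinary correlation is anti-conservative on pooled rows and weak on one change per person

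*Combined protocol and SAP*

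**What the plan says.** Objective 1 (B4) has two halves. The second asks "if changes in circulating microRNA are reflective of changes in skeletal muscle microRNA". Hypothesis 1 expects that "these changes in skeletal muscle microRNA will be associated with modulation in circulating" microRNA. Hypothesis 2 has an association clause too: "Increased efficiency will be associated with higher phosphorylation of IRS-1 and AMPK".

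B5.8.2 gives a repeated-measures mixed model for time, carbohydrate intake and their interaction. It is applied to each outcome in turn, at baseline and "immediately, 3-hr, and 24-hr post glycogen depletion". For relationships between outcomes it gives one sentence: "Correlation coefficients and multiple regression analysis will" "be used to evaluate relationships between study outcome measures". It adds that alpha will be adjusted for multiple comparisons.

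B5.4 (mRNA and microRNA Expression) sets the order of work. "Following identification of skeletal muscle microRNA that had a significant change", those microRNA are measured in serum for their "potential use as noninvasive markers of altered carbohydrate metabolism following glycogen depletion and repletion". The same section sends the reader to the statistical section for the fold-change method, but B5.8 does not describe it.

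**The concern.** The mixed model tests the group response within each tissue. It does not test whether a person's serum follows that person's muscle. That question rests on the correlation and regression sentence, which does not say whether levels or changes enter, how many rows each person contributes, or how dependence among a person's rows is handled. The reference sample for a change is also undefined.

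Ordinary correlation on pooled rows counts repeated samples from 12 people as independent. Ordinary correlation on one change per person is valid but discards most of the data. An unstated choice could therefore yield a serum marker from unrelated tissues or miss a real one. The alpha adjustment helps with neither, because it presumes that each p-value is valid.

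Two questions also remain unseparated: tracking that includes the group depletion and repletion response, and person-specific tracking beyond it. Only microRNA that changed significantly in muscle go to serum, so a group response is expected and the two answers can differ.

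**Working it through.** **The plan's own figure.** B5.8.1 gives 9 per group for 1.5 ± 1 at alpha 0.05 and 80% power. A two-sided two-sample t-test at d = 1.5/1 needs 8.06, hence 9 (power 79.7% at 8, 84.8% at 9). The figure reproduces, but it concerns the difference between arms. The plan gives no figure for the association.

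**Inputs.** 12 volunteers (B5.2.2); two arms (B5.3); four analysed times (B5.8.2). Levels: 12 × 2 × 4 = 96 pairs. Changes from each visit's baseline: 12 × 2 × 3 = 72. The documents give no variance shares, so those are assumed and shown as ranges. Tests are two-sided at 5%. Tissues are unrelated unless r is stated. Rates are from simulation with total variance 1: 20,000 replicates for the ordinary correlations, 8,000 for the within-visit slope except where noted.

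**Significance thresholds.** Critical |r| = t/√(t² + N − 2):
- N = 96: 0.201
- N = 72: 0.232
- N = 24: 0.404
- N = 12: 0.576

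**Pooled changes (72 rows).** With a constant person effect, two changes in one visit share a baseline. Their variance is 2σ² and covariance σ², so they correlate 0.5 in each tissue. The variance of r inflates by 1 + 2 × 0.5 × 0.5 = 1.5, so effective N = 72/1.5 = 48. Then 0.232 × √48 = 1.61, a two-sided tail of about 11%. Simulation gives 10.8–11.3%. This does not depend on the between-person share, which subtraction removes. If person-specific time courses take 0.3/0.5/0.7 of within-visit variance, the rate is 12.4/15.0/19.0%.

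**Pooled levels (96 rows).** Effective N = 96/(1 + 7 × share²), which is 58.9/34.9/21.7 at shares 0.3/0.5/0.7. At 0.5, 0.201 × √34.9 = 1.19, a tail of about 23–24%. Simulated rates at shares 0/0.2/0.3/0.5/0.7 are about 5/8/12/23/36–37%.

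**Narrower choices.**
- One time, both arms (24 rows): levels 5–11% over the same shares; changes 5% with a constant person effect and 6–11% with person-specific courses.
- One change per person (N = 12): about 5%, with power of about 15–16% at r = 0.3 and 40% at r = 0.5.

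**A participant term alone is not enough.** Pooled changes still give 11–12%, because the shared baseline belongs to the visit. On levels, if both tissues shift by an assumed 1 SD at two of the four times with no person-level link, a participant term without time is significant in about 95% of runs at share 0.5.

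**Within-visit slope on the 96 pairs.** With 24 visit intercepts, time and time-by-arm, df = 96 − 24 − 3 − 3 − 1 = 65.

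| Test | False-positive rate | Power at r = 0.3 / 0.5 (independent residuals) |
|---|---|---|
| t on 65 df | 5.1% independent; 5.8–8.5% serial correlation; 6.1–11.2% person-specific courses | 71% at r = 0.3 |
| Whole-participant permutation | 4.8–5.2% | 69% / 99% |
| Participant jackknife, 11 df | 4.3–4.9% | 59.5% / 97% |

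With person-specific courses at 0.5, permutation power is 61%/98%.

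These null runs contain no shared time-by-period effect. When one was assumed in both tissues (immediate-post sample of the second visit, share 0.5, 2,000 replicates), permutation without such a term rejected in 6/8/13% at 0.5/0.75/1.0 SD. Adding time-by-period takes 3 df (65 − 3 = 62). The rates above were not rerun with it.

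**With and without time terms.** Take a shared course only (assumed 1 SD immediately post, 0.5 SD at 3 h) and no person-specific link. The slope without time terms is significant in 32% (share 0) to 76% (share 0.5); with them, in 5%. The first figures are detection of the group response, not false positives.

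**Hypothesis 2 (one value per arm assumed, 24 rows).** Pooled rows give 5.0/6.0/7.7/11.1% at shares 0/0.3/0.5/0.7. A participant term leaves 24 − 12 − 1 = 11 df: 4.6–5.0%, critical |r| 0.553, power 44% at r = 0.5. If both outcomes shift by an assumed 1 SD between diets with no person-level link, that test is significant in 19/30/44/73% at the same shares unless arm is included.

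**The case against.** The sentence in B5.8.2 is generic, does not name serum against muscle, and is silent on model terms. Multiple regression can carry participant or visit terms, and one change per person would be valid. A reader might infer that the plan will pool all rows or has ruled out a participant term. The documents support neither reading.

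The largest rates, 23–37%, are for levels at assumed shares of 0.5–0.7, whereas Objective 1 asks about changes. The paired times are also not missing: B5.8.2 lists the same four for muscle and circulating microRNA, and B5.3 and B5.4 place biopsies and blood draws there. On this view a line naming the rows would suffice, and the choice of permutation or jackknife is a matter of taste.

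Most of this stands. It limits the claim to an unstated unit of analysis with conditional consequences, and it leaves the choice of participant-level inference open. It does not show that a line naming the rows is enough. Of the ordinary correlations examined, those on pooled rows can be anti-conservative, and the one on a single change per person has little power. The same data support a method that is better on both counts.

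**Conclusion.** The concern holds as a gap in specification with material consequences. The half of Objective 1 on serum as a reflection of muscle has no stated unit of analysis, and the named method performs poorly on obvious choices of rows. For changes, which the objective asks about, pooling gives about 11% at a nominal 5% with a constant person effect and independent residuals. It gives 12–19% under the assumed person-specific courses. For levels the range is 5–37%, starting at no inflation. One change per person controls error but would miss most associations at r = 0.3.

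It would be wrong to read 23–37% as the trial's false-positive rate, or to conclude that a participant term alone repairs the analysis. The group-response mixed model and the stated sample size are unaffected. The point should be settled before the serum analysis, because the marker claim depends on it.

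**What to change.** For each microRNA carried to serum, replace the ordinary correlation with a within-person association of log2 muscle and log2 serum expression at the four paired times, by repeated-measures correlation or a mixed model. Then:

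- Include an intercept for each of the 24 person-by-arm visits, time, time-by-arm, and time-by-period where estimable.
- Use inference with the participant as the unit, such as whole-participant permutation or a participant-level jackknife on 11 df.
- If a version without time terms is also reported, label it as including the group depletion and repletion response.
- Apply the stated multiplicity adjustment across the microRNA tested.
- Define the reference sample for fold change.
- For Hypothesis 2, include a participant term and report the association with and without arm, each labelled, because without arm a shared diet effect alone produces an association.

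The cost is a paragraph of SAP text and more model code; no new data are needed. B5.2.2 plans complete data on 12 volunteers, which suits the permutation. Fewer associations will be called significant than with pooled rows. Against the 65-df test, permutation lowers power at r = 0.3 from 71% to 69% with independent residuals, and from 68% to 61% with person-specific courses. The Hypothesis 2 test stays weak.
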